#### 5. PROCEDURE

#### 5.1 Introduction

[figure not shown]
- 5.1.1 This Statistical Analysis Plan (SAP) is based on the study protocol final version V1.4, dated 4 March, 2018.
- 5.1.2 This Statistical Analysis Plan (SAP) contains details of the statistical analyses that will be performed, providing a more detailed description of the approach defined in the study protocol. Definitions of variables and populations used for the analyses are also included. The SAP will be finalized and signed prior to hard lock of the database.
- 5.1.3 General output specifications are provided; examples are given of calculations of derived variables.

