Study Day a	Day a -(- 28) throug h Day (-7)	Day a -(- 14) through Day (-2)	Day (-1)	Day a 0	Da y 1	Da y 3	Da y 7	Day 14	Da y 21	Da y 28	Day 56, 84, 112, 140, 168
MRI section around the umbilicus – for 3 rd and 4 th cohort or in cohort 2 if 2 subject experience intolerable side effects in cohort 3)											Every 28 days
Anthropometri c measurements: (weight, height) BMI, (waist & hip circumference) WHR	X	X	X							X	Every 28 days
Weight – by the subjects at home –							X	X	X		On weeks when

Medi Stat Statistics in Medicine	DOCUMENT NUMBER: 050-BST-PLN-001	PAGE: 18 of 31
TITLE: Statistical Analysis Plan		EFFECTIVE DATE: 14/Nov/2018 REVISION NUMBER: 2.0

[figure not shown]
Study Procedure	Screening Day 1	Screeni ng Day 2	Clinic Admissi on	Baseline (Treatme nt)	Visit Schedule (Days 1 to 28)			8)	Follow- up Schedu le for the highest dose cohorts (Days 29 - 168)		
Study Day a	Day a -(- 28) throug h Day (-7)	Day a -(- 14) through Day (-2)	Day (-1)	Day a 0	Da y 1	Da y 3	Da y 7	Day 14	Da y 21	Da y 28	Day 56, 84, 112, 140, 168
morning(8- 12hr overnight fast) and evening											not visiting the site
Urine Drug Screen	X		X								
Infra-Red thermal imaging of the injected site	X		X		X		X	X	X	X	On Day

Medi Stat Statistics in Medicine	DOCUMENT NUMBER: 050-BST-PLN-001	PAGE: 19 of 31
TITLE: Statistical Analysis Plan		EFFECTIVE DATE: 14/Nov/2018 REVISION NUMBER: 2.0

Study Procedure	Screening Day 1	Screeni ng Day 2	Clinic Admissi on	Baseline (Treatme nt)	Vi	isit Scl	nedule	(Days	s 1 to 2	8)	Follow- up Schedu le for the highest dose cohorts 1 (Days 29 - 168)
Study Day a	Day a -(- 28) throug h Day (-7)	Day a -(- 14) through Day (-2)	Day (-1)	Day a 0	Da y 1	Da y 3	Da y 7	Day 14	Da y 21	Da y 28	Day 56, 84, 112, 140, 168
Infra-Red thermal imaging of the injected site - for 3 rd and 4 th cohort or in cohort 2 if 2 subjects experience intolerable side effects will in cohort 3) k											Every 28 days
Serum Chemistry, Hematology c	X		X		X	X	X	X		X	
Histamine levels d			X		X	X		X			
Urinalysis  Pharmacokinet ics f	X			Pre e X post e	X			X		X	

Medi Stat Statistics in Medicine	DOCUMENT NUMBER: 050-BST-PLN-001	PAGE: 20 of 31
TITLE: Statistical Analysis Plan		EFFECTIVE DATE: 14/Nov/2018 REVISION NUMBER: 2.0

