- f. Pharmacokinetics at the given time points: 0, 30, 60 min, 2h, 3h, 4h, 6h, 8h, 12h, 16h, 24h, 30h in subjects from the 1st, 2nd and 3rd cohorts. Pharmacokinetics will not be conducted in the fourth cohort as the injected dose is divided in 2 clusters 2 weeks apart.

Medi Stat Statistics in Medicine	DOCUMENT NUMBER: 050-BST-PLN-001	PAGE: 22 of 31
TITLE: Statistical Analysis Plan		EFFECTIVE DATE: 14/Nov/2018 REVISION NUMBER: 2.0

- g. Draize score evaluation: before injection, 2h, 24h and 7d,14d,21d and 28d following injection
- h. Vital signs measurement: before injection, 2h, 24h and 7d,14d,21d and 28d following injection
- i. ECG is to be performed in triplicate for all measurements in given time point: 4h, 12h, 24h, Day 14 and 28 following injection
- j. Pulse rate measurements at given time points: 1h, 2h, 4h, 8h, 12h, 24h following injection in the opposite hand of blood sampling
- k. For 3 subjects of cohort 3 (in cohort 2 if 2 subjects experience intolerable side effects in cohort 3) if thermogenesis is evident by thermal camera by Day 56, biopsy from the injected for histology and BAT characterization.
- 1. For subjects from the 3rd (or in cohort 2 if 2 subjects will experience intolerable side effects within the 3rd cohort) and 4th cohort

Medi Stat Statistics in Medicine	DOCUMENT NUMBER: 050-BST-PLN-001	PAGE: 23 of 31
TITLE: Statistical Analysis Plan		EFFECTIVE DATE: 14/Nov/2018 REVISION NUMBER: 2.0

- 5.4.5 Randomization, Blinding and Un-blinding
- 5.4.6 Subjects will be randomized to each study group, i.e., investigational therapy or control, left side injection or right side injection according to a predefined randomization scheme. The investigational therapy group will be treated with RZL-012 and the control group will be treated with the same formulation (vehicle) as with RZL-012, absent active medication
- 5.4.7 Masking will be used to blind the Investigator regarding randomization, i.e., assignment to study group will be disclosed only after subject eligibility is confirmed and immediately before treatment initiation. The pharmacist will be unmasked and will be responsible to fill the syringes for injection.
- 5.5 Selection of study population
  - 5.5.1 Study Population
  - 5.5.2 Male subjects
  - 5.5.3 Age 20 60 years old
  - 5.5.4 The study population include subjects who are obese by Body Mass Index (BMI) definition (27.5 < BMI ≤ 34.9)
  - 5.5.5 Rationale Sample Size Calculation

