  - 5.5.6 The planned sample size is 32 subjects (8 in each cohort). 6 subjects per dose group paradigm with the addition of a 2 subjects per control group for all doses. A maximum of 32 evaluable subjects will be included in the study (24 in the RZL-012 treatment arm and 8 in the placebo arm) and followed for as long as 3 months in the 2 lowest dose cohorts, and in the 2 highest dose cohorts for up to 5 months.
- 5.6 Statistical Analysis Software and Data Management
  - 5.6.1 Data manipulation, tabulation of descriptive statistics, calculation of inferential statistics, and graphical representations will be performed using SAS® version 9.3 or higher for Windows. If the use of other software is warranted, the final statistical methodology report will detail what software was used for what purposes.
  - 5.6.2 Data Management
  - 5.6.3 Data management for the study is performed by Spaulding Clinical.
  - 5.6.4 Medical Coding

- 5.6.5 Concomitant medications entered into the database are coded using the WHO (World Health Organization) Drug Public Website Dictionary named WHOCC-ATC/DDD index, which employs the Anatomical Therapeutic Chemical classification system.
- 5.6.6 Adverse events are coded using the most updated version of Medical Dictionary for Regulatory Activities (MedDRA) terminology.
- 5.6.7 Medical history events are coded using the most updated version of Medical Dictionary for Regulatory Activities (MedDRA) terminology
- 5.6.8 Handling of Missing data
- 5.6.9 No imputation of missing data will be performed
- 5.6.10 Protocol Violations and Deviations
- 5.6.11 Departures from the protocol should be avoided unless required for the safety of the subject. Protocol deviations and, if possible, the reason for occurrence will be documented by the study monitor and included in the final clinical study report.
- 5.6.12 The Investigator must report any protocol deviation to the Sponsor and, if required, to the IRB/IEC in accordance with local regulations, within reasonable time. All violations and deviations must be recorded in the study site's electronic system and signed by the Investigator (or designee).

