## 5.8 Statistical Analysis

- 5.8.1 General
- 5.8.2 All measured variables and derived parameters will be listed individually and, if appropriate, tabulated by descriptive statistics. For categorical variables summary tables will be provided giving sample size, absolute and relative frequency. For continuous variables summary tables will be provided giving sample size, arithmetic mean, standard deviation, standard error, coefficient of variation (CV%), median, minimum and maximum of variables, and 95% confidence intervals of means.
- 5.8.3 The data is analyzed using the SAS ® version 9.3 or higher (SAS Institute, Cary North Carolina). Analyses presented in the clinical report but not mentioned in the SAP are unplanned or ad-hoc analyses.
- 5.8.4 Statistical methods presented in the SAP may be slightly different from those that are presented in the protocol. Differences are clearly stated and the SAP supersedes the protocol only with regard to the way data will be handled and analysed.
- 5.8.5 Derived Data
- 5.8.6 Definition of baseline
- 5.8.7 Baseline is defined as the last non-missing value prior to the patient start of treatment (screening or baseline visit).
- 5.8.8 End of Study
- 5.8.9 The end-of-study visit is defined as Day 168.
- 5.8.10 Disposition of subjects (Table 14.1-1 14.1.2)
- 5.8.11 The number of subjects that are randomized into the study, the number of subjects in the Safety, efficacy analysis set, and PK populations, and the number of study completers will be presented.
- 5.8.12 The reasons for early termination/ withdrawal will be summarized.

- 5.8.13 Demographic and Baseline data (Tables 14.1-3-14.1-4)
- 5.8.14 Baseline and demographic data will be summarized in appropriate tables using the Safety population. The data includes demographic characteristics (age and gender) and medical history.
- 5.8.15 Efficacy Analysis
- 5.8.1 The primary endpoint for efficacy is a significant thermogenesis at the injected site compared with the contra-lateral, non-injected site.
- 5.8.2 The average temperature will be presented in a tabular form by visit, side (treated / not treated) and treatment received (RZL-012 / placebo) by cohort and overall. Difference between the sides (treated not treated) will be presented in a tabular form by visit treatment along with the change from baseline (net-delta) in these differences by cohort and overall.

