- 5.8.3 Kruskal-Wallis will be used to compare the net-delta between the study arms for the relevant cohorts and visits.
- 5.8.4 The number and percent of subjects with a thermogenic effect, defined as a net-delta ≥ 1, will be presented by cohort and visit for the subjects in the active arm. The duration of the thermogenic effect after the Day 28 visit, for subjects in the active arm with thermogenic effect at the Day 28 visit will be presented.
- 5.8.5 Subcutaneous Fat Mass (SFM) ratio (treated sites / control sites) averaged over the MRI slices will be presented in tabular form by visit, treatment and cohort. The change from baseline in this ratio (in % from the ratio at baseline) will be presented in the same manner, and compared between the treatment arms with Kruskal-Wallis test.
- 5.8.6 Changes from baseline in fasting blood glucose, lipid profile, anthropometric changes, inflammatory markers and cytokines will be presented by visit, treatment, and cohort.
- 5.8.7 Histology results will be presented in tabular form by treatment for relevant subjects.
- 5.8.8 Safety analysis
- 5.8.9 Safety data will be summarized for the Safety population.
- 5.8.10 Adverse events will be coded according to coding dictionaries (the most updated version of MedDRA) and presented in tables by System Organ Class (SOC) and Preferred Term (PT) and by treatment group.

- 5.8.11 The incidence of AEs, as well as the intensity and relationship to study drug will be summarized by treatment group.
- 5.8.12 The incidence of all adverse events will be presented by treatment overall and by cohort along with two sided 95% exact binomial Confidence Interval (CI).
- 5.8.13 The incidence of intolerable side effects will be presented by treatment overall and by cohort along with two sided 95% exact binomial Confidence Interval (CI).
- 5.8.14 Concomitant medication verbatim terms (as recorded on the CRFs) will be coded to Anatomical Therapeutic Chemical (ATC) Level 2 and 4 using the World Health Organization (WHO) dictionary.
- 5.8.15 Interim Analysis
- 5.8.16 An interim analysis is planned at the end of each cohort for evaluation of efficacy. For this purpose, a data lock (except for externally collected data such as PK) will be implemented after each cohort is completed. Upon lack of trends in efficacy due to effect size, the Sponsor will consider study termination

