14.2 Efficacy Assessment

14.2.1 Primary Safety Endpoint

Table 14.2.1-1: Summary of Thermal Imaging per visit

Table 14.2.1-2: Summary of Thermal Imaging Changes per visit

P-value for difference between groups

Table 14.2.1-3: Frequency of Thermogenic Effect

Table 14.2.1-4: Duration of Thermogenic Effect

Table 14.2.1-5: Summary of MRI Results

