16.2.6 Individual Efficacy/PK/PD Response Data

Listing 16.2.6-1: PK Collection

Listing 16.2.6-2: Thermogenesis results

Listing 16.2.6-2: RZL-012 Concentration (ng/mL) by Subject, Treatment and Time

Listing 16.2.6-3: RZL-012 PK Parameters by subject and Treatment

Listing 16.2.6-5: MRI results

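### The SAP presents duration of thermogenic effect with no rule for an effect still present at the last image, although the imaging schedule caps recordable duration at 28 days in cohorts 1–2 and 140 days in cohorts 3–4

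*SAP*

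**What the plan says.** SAP item 5.8.4 under Efficacy Analysis (the number occurs twice in section 5.8) defines the effect as a net-delta of at least 1. It says that duration after Day 28, "for subjects in the active arm with thermogenic effect at the Day 28 visit will be presented". The output is a title only, "Table 14.2.1-4: Duration of Thermogenic Effect". Protocol 10.5.5 has the same sentence and no further method.

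Three neighbouring rules come close to the point:

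- SAP 5.8.2 (General) has variables listed individually and, where appropriate, tabulated. For continuous variables the tables give "arithmetic mean, standard deviation, standard error, coefficient of variation (CV%), median, minimum and maximum of variables, and 95% confidence intervals of means".
- SAP 5.6.9 states: "No imputation of missing data will be performed".
- SAP 5.8.9 sets one end-of-study visit, Day 168, for every cohort.

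The imaging window depends on dose. Protocol 6.1.12, 6.1.17.2.1 and Table 2 end thermal imaging at Day 56 in the lower-dose cohorts. Cohorts 3–4 continue every 28 days, on Days 56, 84, 112, 140 and 168, as a maximum. The SAP schedule (5.4.4) keeps a separate 28-day imaging row for cohorts 3–4, with the exception "cohort or in cohort 2 if 2 subjects experience intolerable side effects will in cohort 3". The base case below is the one in which that exception does not apply.

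**The concern.** A responder in cohort 1 or 2 has one image after Day 28. A responder in cohort 4 can have five. If the effect is still present at the last image, the true duration is known only to exceed the time observed, and the plan does not say what to enter. Two simple choices are open: record the effect as ending at the last image, or leave the duration missing. Either way the tabulated value depends on the imaging schedule as well as on the drug, and the schedule differs by dose.

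This matters because protocol 10.1 describes a search for the tolerated dose with the largest thermogenic effect, and duration is the first secondary endpoint listed. Protocol 1.2.4 already expects higher doses to do better. The artefact runs in that direction, so it could be read as confirmation.

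**Working it through.** **Schedule, from the documents.** Last image in cohorts 3–4: 28 + 5 × 28 = Day 168, which matches protocol Table 2. Last image in cohorts 1–2: 28 + 28 = Day 56, which also matches. The longest recordable duration after Day 28 is 56 − 28 = 28 days against 168 − 28 = 140 days, a five-fold difference that needs no model.

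**Illustration, with assumptions.** The documents give no persistence figure. Assume that every dose has the same persistence after Day 28, exponential with mean m = 42, 84 or 168 days. The chance that the effect lasts from one image to the next is p = exp(−28/m). Cohort 4 represents the long schedule, since no biopsies are planned there.

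*Ongoing effects recorded as ending at the last image* (duration = last visit with effect minus Day 28):

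- cohorts 1–2: 28p
- cohort 4: 28(p + p² + p³ + p⁴ + p⁵)

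| m (days) | p | Cohorts 1–2 | Cohort 4 | Ratio | Ongoing at last image, cohorts 1–2 (p) | Ongoing at last image, cohort 4 (p⁵) |
|---|---|---|---|---|---|---|
| 42 | 0.513 | 14.4 | 28.5 | 1.98 | 51% | 4% |
| 84 | 0.717 | 20.1 | 57.4 | 2.86 | 72% | 19% |
| 168 | 0.846 | 23.7 | 87.3 | 3.68 | 85% | 44% |

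*Ongoing effects left missing.* Cohorts 1–2 contribute only losses seen at Day 56, so everyone who counts has 0 days. Cohort 4 gives Σ 28j·pʲ(1 − p)/(1 − p⁵) for j = 0 to 4, which is 24.4, 38.2 and 46.8 days. Counting to the first visit without effect adds 28 to each: 28 days against 52.4, 66.2 and 74.8.

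**How often the false ordering appears.** Ongoing effects are taken as ending at the last image. The figures for six and three responders come from 200,000 simulated cohorts. With one responder per cohort the chance is exact: (1 − p)p + p³.

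| Day 28 responders per cohort | m = 42 | m = 84 | m = 168 |
|---|---|---|---|
| 6 | 75% | 95% | >99% |
| 3 | 61% | 84% | 96% |
| 1 | 39% | 57% | 74% |

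Entries are the chance that cohort 4's mean exceeds cohort 1's although persistence is equal. With one responder the reverse ordering has chance p(1 − p) = 25%, 20% and 13%; the rest are ties.

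**The same data compared at Day 56.** With six responders per cohort, the proportion still at net-delta ≥ 1 is higher in cohort 4 in 39%, 37% and 34% of simulated trials and lower in 39%, 37% and 33%. The false trend disappears.

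**The case against.** The best reply is that the plan already offers a fair view. The same SAP item presents the number and percent of active subjects with an effect by cohort and visit, in Table 14.2.1-3, so Day 56 can be compared across all doses. Individual values are also listed ("Listing 16.2.6-2: Thermogenesis results"), and the protocol states the unequal windows openly. This stands and lowers the stakes. It does not supply a duration rule, and that percentage is of all active subjects rather than of Day 28 responders.

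Second, a reader might infer that the SAP commits itself to mean durations by cohort. It does not. The descriptive statistics apply where appropriate, and the duration sentence, unlike its neighbours, does not mention cohort. The printed maximum would also show the 28-day ceiling if ongoing effects were recorded as ending at the last image. Means are a likely outcome, not a certain one.

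Third, the magnitudes rest on chosen means, equal persistence over a 4.5-fold dose range (180/40), and a set number of responders. In phase 0 the temperature rise was mostly seen at the highest dose, at Day 14 or 21, so low-dose Day 28 responders may be few. This stands; with few responders the false ordering is much less reliable.

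Fourth, a reader might infer that cohort 3 will certainly look shorter-lasting than cohort 4 because of the biopsies. The SAP schedule makes the biopsy depend on the effect: "if thermogenesis is evident by thermal camera by Day 56, biopsy from the injected for histology and BAT characterization". But the statement that biopsied subjects leave 7 days later is in protocol 6.1.14 of the supplied version, 001.2, and the SAP says: "This Statistical Analysis Plan (SAP) is based on the study protocol final version V1.4, dated 4 March, 2018". Whether the exit still applies cannot be told from these documents.

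Finally, the synopsis wording that ties later follow-up to a persisting effect might be taken as a further bias. Loss of effect seen at a visit is an observed end of duration, so it does not distort this result.

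**Conclusion.** The gap is real. The SAP has no rule for effects ongoing at the last image, and in the base case the schedule alone allows 28 days in cohorts 1–2 and 140 in cohorts 3–4. If duration is tabulated with the usual statistics, equal persistence looks about 2.0-, 2.9- and 3.7-fold longer on the long schedule under the assumed means. Leaving ongoing effects missing gives a similar distortion. The five-fold ceiling comes from the documents; the ratios are illustrative.

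It would be wrong to read this as a threat to the efficacy conclusions. Duration is descriptive and secondary, no test of it is planned, and the Day 28 primary result is untouched. Day 56 as the last low-dose image is taken from the protocol, because the number is not legible in the SAP schedule as available. A rule in V1.4 cannot be excluded, but the SAP, which presents itself as the more detailed text, has none. This lies between a minor point and one that should be fixed, and is best treated as a cheap improvement.

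**What to change.** In the Efficacy Analysis item 5.8.4 of the SAP:

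1. Define duration as time from Day 28 to the first visit with net-delta below 1, right-censored at the last image.
2. Flag subjects whose effect is ongoing at the last image. In Table 14.2.1-4 show a censored summary or listing by cohort, instead of means with confidence intervals of means.
3. Base any statement across doses about persistence on Day 56, which protocol 10.5.2 already names as an analysis time for all dose levels. Use the proportion of Day 28 responders still at net-delta ≥ 1.
4. Check V1.4. If it keeps the exit of biopsied cohort 3 subjects, censor them at Day 56 and identify them in the table.

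The cost is a few SAP sentences and one changed table shell. No subjects, visits or procedures are added, and the no-imputation rule stays. The drawbacks are that summaries will be coarse with at most six active subjects per cohort, and late results may look less favourable.

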#### Results:

This was a dose escalation exploratory clinical trial of RZL-012, a first-in-class, new chemical entity.

RZL-012 was generally found to be safe in all cohorts. There were no clinically significant changes in vital signs, ECG and almost all blood laboratory tests. Most AEs associated with RZL-012 injection occurred confined to the injection site and were transient. Biopsy from the injected site revealed no damage to the skin 56 days following RZL-012 injection. The only significant local AE was an abscess in one subject in the lower abdomen on the injected side, but at a considerable distance from the site of injection.

In another patient, a severe elevation of ALT blood levels and a moderate elevation of AST blood levels were seen 14 days following injection. This elevation was transient (resolved within 14 days). In light of the pre-clinical findings (increased AST blood levels in female rats sacrificed on Day 2 following RZL-012 injection) and in light of the findings in this clinical trial, Raziel therefore plans to monitor closely (on 24hr, Day 3, Day 7, Day 14, Day 21, Day 28 and will follow further if necessary) liver functions in the next clinical trial. There were no other systemic clinically significant AEs.

The exploration of thermogenesis induction by RZL-012 in humans was successful. A raise in temperature at the injection site was mostly evident in cohort 3 (the highest dose) at Day 14 or Day 21 following injection in RZL-012 treated subjects only. This change in temperature was captured and recorded by the infra-red camera.

Although not statistical significant, a drop in the change from baseline in Subcutaneous Fat Mass (SFM) ratio (treated/control) over time by MRI in RZL-012 treated subject of cohort 3 was evident in 5 of 6 treated subjects. The drop in subcutaneous fat associated with a drop in weight (more than 1 kg) and BMI when compared to baseline and is evident in 4 of 6 RZL-012 treated subjects of cohort 3 on Day 28 and/or Day 56, while controls gained weight and increased BMI.

Biopsy did not yield enough tissue (because punch biopsy did not penetrate deep enough to reach the remodeled tissue), and therefore, it was not possible to demonstrate that thermogenesis is due to adipose tissue remodeling by.

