### 6.1.17.2.4. Anthropometric Measurements Change

Anthropometric measurements will be evaluated comparing to baseline. Anthropometric measurements changes are defined as significant reduction in body weight, BMI and WHR at the end of the study compared to baseline.

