#### 10.5. STATISTICAL ANALYSIS

#### 10.5.1. General

Statistical analysis will be performed using SAS V9.4 or higher (SAS Institute, Cary NC, USA).

Statistical analyses will be mainly descriptive in nature where study data will be tabulated and summarized using the mean, standard deviation or standard error, median, minimum, maximum and number of subjects by cohort for continuous data. For categorical data, results will be summarized via a count and percentage by cohort. The effects of noncompliance, dropouts, and covariates, may be assessed to determine the impact on the general applicability of results from this study.

If any statistical tests are performed, they will be two-sided. The required significance level of findings will be equal to or lower than 5%. Nominal p-values will be presented.

Where confidence limits are appropriate, the confidence level will be 95%.

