- 5.4.2 This is a consecutive 4 cohort, dose escalation placebo-controlled clinical trial in overweight and obese subjects. All cohorts will be comprised of 6 active (RZL-012) and 2 placebo subjects.
- 5.4.3 Within each cohort, dosing of the first 3 subjects will progress consecutively from one individual to the other at 7-day intervals. For additional precaution, the first 3 subjects will be forced randomized into 2 active and 1 control. This study design will allow the physicians to monitor safety in a two subjects at each dose, nevertheless the blindness will remain intact. The remaining subjects in a cohort will be randomized to either active treatment or placebo in a ratio determined by the number of subjects targeted for each cohort. Dosing of the next subjects will be in couples and the last subjects will be in a triplet.

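### Weight, BMI, WHR, glucose and lipids have no planned RZL-012 versus vehicle estimate, and the weight, BMI and WHR criterion refers only to the subject's own baseline

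*SAP*

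**What the plan says.** **Endpoint definition.** Protocol 6.1.17.2.4 says anthropometric changes are "defined as significant reduction in body weight, BMI and WHR at the end of the study compared to baseline". Vehicle is not mentioned and the meaning of significant is not given. Protocol 6.1.17.2.3 also compares laboratory values, including glucose and lipids, with baseline, but by the investigating physician's view of normal ranges and medical status.

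**Planned analysis.** Protocol 10.5.5 and SAP 5.8.6 (Efficacy Analysis; the SAP uses the numbers 5.8.1 to 5.8.15 twice) say "Changes from baseline in fasting blood glucose, lipid profile, anthropometric changes, inflammatory markers and cytokines will be presented by visit, treatment, and cohort". In the same block, SAP 5.8.3 and 5.8.5 plan Kruskal-Wallis comparisons between arms for net-delta and for the subcutaneous fat mass (SFM) ratio. Temperature is also tabulated overall across cohorts; the measures in 5.8.6 are not.

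**General rules.** Protocol 10.5.1: "Statistical analyses will be mainly descriptive in nature", and "If any statistical tests are performed, they will be two-sided", at a 5% level with nominal p-values. The SAP's general section (5.8.2) gives 95% confidence intervals of means for continuous variables. Its 5.8.3 classes any analysis not mentioned in the SAP as unplanned or ad hoc.

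**Design and shells.** SAP 5.4.2: "All cohorts will be comprised of 6 active (RZL-012) and 2 placebo subjects". The table list in SAP Appendix I has one line for a between-group p-value, under the thermal imaging change table. It has glucose and lipid tables among the safety outputs, and none for weight, BMI or WHR.

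**The concern.** The trial is randomized against vehicle, so the effect of RZL-012 on weight or lipids is the difference between arms in change from baseline. A mean change in the RZL-012 arm alone estimates the drug effect plus whatever moves everyone: repeat measurement, fasting visits, weekly weighing, season. A criterion tied to own baseline can credit the drug with a shared fall, or miss a benefit that a shared rise offsets.

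These are named secondary efficacy endpoints (protocol 4.2 and 10.2.3). As the SAP stands, the vehicle subjects are shown descriptively only. A later arm comparison would carry the ad hoc label under the SAP's own general rule.

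**Working it through.** **1. Inputs.** The sample size reproduces as a count: 4 × (6 + 2) = 32, with 4 × 6 = 24 RZL-012 and 4 × 2 = 8 vehicle. Alpha is two-sided 5% (protocol 10.5.1). The documents give no SD, expected effect or drift for these measures, so everything below is in SDs of the change from baseline, and the drift sizes are assumptions.

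**2. Baseline-only rule with no drug effect.** Suppose the criterion were applied as a two-sided one-sample t-test and both arms shift by d SD. The probability of significance is P(|T| > t(0.975, n − 1)), where T is non-central t with n − 1 degrees of freedom and non-centrality d√n. The critical value is 2.571 for n = 6 and 2.069 for n = 24. For example, d = 0.5 gives non-centrality 0.5 × √6 = 1.22 and 0.5 × √24 = 2.45.

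| Common drift (SD) | One cohort, n = 6 | Pooled, n = 24 | RZL-012 v vehicle |
|---|---|---|---|
| 0.2 | 6.9% | 15.6% | 5% |
| 0.3 | 9.3% | 29.1% | 5% |
| 0.5 | 17.1% | 65.0% | 5% |

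The n = 6 column matches the planned by-cohort layout. The n = 24 column needs pooling that SAP 5.8.6 does not plan. The last column is 5% at any drift because a common shift cancels in the difference; a simulation of 24 v 8 at 0.5 SD gave 5.0%.

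**3. Masking.** If a 1.0 SD drug effect meets an equal and opposite common shift, the net change in the active arm is zero. The baseline-only rule then finds it 5% of the time. A 24 v 8 t-test finds it 66% of the time.

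**4. Do side-by-side tables supply the contrast?** Each cohort shows 6 v 2. The SE of that difference is √(1/6 + 1/2) = 0.82 SD and the 95% CI half-width is 2.00 SD. The smallest exact two-sided rank p-value is 2/C(8,2) = 2/28 = 0.071.

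Later visits are thinner. SAP 5.8.9 puts end of study at Day 168, which only cohorts 3 and 4 reach if all four cohorts run. One vehicle subject leaves after the Day 56 biopsy (protocol 6.1.14), so at most 4 − 1 = 3 vehicle subjects remain. There may be fewer, because the synopsis continues anthropometry in those cohorts only while a thermogenic effect is apparent.

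**5. What the data can support.** Day 28 weight, BMI, WHR, glucose and lipids are scheduled for every subject (protocol Table 2). For 24 v 8 the SE is √(1/24 + 1/8) = 0.41 SD, against √(1/24) = 0.20 SD within the active arm. The 95% CI half-width is 2.042 × 0.408 = 0.83 SD, and the difference detectable with 80% power is 1.18 SD.

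**The case against.** The strongest reply is that nothing is being tested wrongly, because nothing is being tested. The documents name no within-arm test for these endpoints and call the statistics mainly descriptive. The tables are split by treatment, so vehicle sits beside RZL-012 and a common shift could be seen. The SAP does not repeat the significant-reduction criterion and says it supersedes the protocol on how data are analysed. It also follows protocol V1.4 of 4 March 2018, whereas the protocol reviewed is 001.2 of 26 May 2017.

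Much of this stands, and it limits the claim:

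- A reader might infer that the plan tests for no time trend in treated subjects. It does not; the error rates apply only if the protocol criterion is used as written.
- A reader might extend them to the laboratory rule in protocol 6.1.17.2.3. That is a physician's judgement about an individual, not a test of an arm mean.
- A reader might take phase 0 as proof of shared drift. It reports that 4 of 6 treated cohort 3 subjects lost more than 1 kg "while controls gained weight and increased BMI". The arms diverged, and with two controls per cohort no drift size can be drawn. It shows only that controls' weight changed.

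What does not stand is that the tables fill the gap. Two unpooled vehicle subjects per cohort, and at most three at Day 168, do not give a usable contrast.

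**Conclusion.** The point holds in a limited form. For weight, BMI, WHR, fasting glucose and lipids, vehicle is shown descriptively only, with no between-arm estimate, interval or test and no pooling of the 8 vehicle subjects. The protocol's criterion for weight, BMI and WHR cannot separate a drug effect from a common shift. To say that a shared shift will be read as a drug effect goes further than the documents, since the tables do show both arms.

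If the criterion were applied at two-sided 5%, a common drift of 0.2 to 0.5 SD with no drug effect would meet it in 7% to 17% of cases per cohort, or 16% to 65% with the active arm pooled, against 5% between arms. These figures rest on the assumed drifts, on normal changes with equal variance, and on counting significance in either direction. The change is worth making, but these are secondary measures in a small, mainly descriptive study.

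**What to change.** - **SAP 5.8.6 (Efficacy Analysis):** add, labelled exploratory, the RZL-012 minus vehicle difference in change from baseline at Day 28 for weight, BMI, WHR, fasting glucose and lipids. Stratify by cohort, give a 95% CI, and show cohort-level values descriptively without by-cohort tests. Keep within-arm changes as description.
- **SAP Appendix I:** add the missing weight, BMI and WHR table shell, and a column for the difference in the glucose and lipid tables.
- **Protocol 6.1.17.2.4:** replace the baseline-only criterion with this contrast. First check whether the wording persists in V1.4, the version the SAP cites.

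No new data are needed. The cost is SAP wording, one new shell and added columns. The interval is about twice as wide as the within-arm one (SE 0.41 against 0.20 SD), and the estimate pools doses from 40 to 180 mg, so it averages over any dose response. It is unlikely to detect a difference much below 1.18 SD, and the report should say so.
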